7.1 Demographic and Baseline Characteristics

Demographics and baseline disease characteristics and UC disease history values will be summarized using descriptive statistics. For the following characteristics marked by '#' the source data from Study M11-290 should be used for analyses (although some of the

items may also have been transferred from Study M11-290 into the Study M10-870 database).

Demographics and baseline characteristics:

• Subject demographics

- Sex# (female, male)
- Age [years] {using birth date#}
- Age categories ($< 13 \text{ years}, \ge 13 \text{ years}$)
- o Race# (White, Black, Asian, American Indian/Alaska Native, and Other)
- Ethnicity# (Hispanic or Latino, Japanese, no ethnicity)
- o Geographic region# (North America, Western Europe, Eastern Europe)
- Body Weight# [kg]
- o Body Weight categories ($< 40, 40 < 60, \ge 60 \text{ kg}$)
- Height# [cm]
- \circ BMI [kg/m²]
- Tobacco/Nicotine Use#* (current user, former user, never, or unknown)
- Alcohol Use#* (current user, former user, never, or unknown)
- * Data from Study M11-290-Baseline, to be clarified in a footnote to the table.

• PPD skin test/QuantiFERON®-TB Gold test/TB prophylaxis#

- Tuberculin PPD skin test (negative, positive), positive defined as ≥ 5 mm
- QuantiFERON-TB Gold test (negative, positive, indeterminate)
- Combined result of Tuberculin PPD skin test and QuantiFERON-TB Gold test
- Enrollment under TB prophylaxis (yes, no)

• Disease characteristics at Baseline

- Duration of UC
 - In months: (Baseline date date of diagnosis of UC# + 1)/(365.25/12)
 - In years: (Baseline date date of diagnosis of UC# + 1)/365.25
- Site of UC# (Left sided UC vs. Extensive UC/pancolitis)

[figure not shown]
- Mayo Score#
- Mayo Score at Study M11-290-Baseline#
- Partial Mayo Score# (PMS)
- o PMS at Study M11-290-Baseline#
- Endoscopy Subscore#
- Rectal Bleeding Subscore#
- Physician's Global Assessment (PGA) Subscore#
- Stool Frequency Subscore#
- Number of stools in the last 24 hours prior to baseline# (i.e., last non-missing value $-1 \le Rx$ Day ≤ 1)
- o PUCAI#
- o PUCAI at Study M11-290-Baseline#
- IMPACT III total score and subscores#
- WPAI# (Absenteeism, Presenteeism, Work Impairment, Activity Impairment)
- o hs-CRP# [mg/L]

7.2 Medical History

Medical history data will be summarized and presented using System Organ Class (SOC) and Preferred Terms (PT) according to the Medical Dictionary for Regulatory Activities (MedDRA) dictionary. The SOCs will be presented in alphabetical order and the PTs will be presented in alphabetical order within each SOC. The number and percentage of subjects with a particular PT will be summarized. Subjects reporting more than one PTs within a SOC will be counted only once for that SOC.

7.3 Prior Treatment and Concomitant Medications

Prior medications are those medications taken prior to the first dose of study drug in Study M11-290. This includes medications with a start date before the first study drug administration date in Study M11-290, regardless of the end date of these medications.

Medications taken on the day of the first dose of study drug in Study M11-290 are not counted as prior medications.

In cases where incomplete or missing medication dates are collected, a conservative approach will be taken such that if a medication could have been a prior medication, it will be counted as a prior medication.

[figure not shown]
Baseline medications are those medications that subjects were on at the time of the first dose of study drug in Study M10-870. This includes medications that started prior to the first dose of study drug in Study M10-870 and continued after the first dose of study drug or ended at the time of the first dose of study drug, as well as, medications that began on the day of the first dose of study drug in Study M10-870.

Concomitant medications are those medications, other than study drug, taken after the first dose of study drug in Study M10-870 and within 14 days of the last dose of study drug in Study M10-870. This includes medications with a start date between first study drug administration and last study drug administration + 14 days, as well as, medications with a start date prior to first dose of study drug and which are ongoing after first dose of study drug in Study M10-870. Medications taken on the day of the first dose of study drug in Study M10-870 are counted as concomitant medications.

In the situation where an incomplete or missing medication date is collected (start or end date), a conservative approach will be taken such that if a medication could have been a concomitant medication, it will be counted as a concomitant medication.

The medications will be coded by WHO DRUG dictionary. The number and percentage of subjects who had taken medications will be summarized by generic drug name for all medications as well as for those flagged as UC-related medications. No statistical tests will be performed.

The number and percentage of subjects with prior (prior to Study M11-290) anti-diarrheal therapy, NSAIDs, biologic DMARDs, synthetic DMARDs, IBD related antibiotics, anti-TNF biologics, non-anti-TNF biologics, systemic corticosteroids and among those the oral

corticosteroids, IMM and aminosalicylates will be summarized. In addition, four groups of baseline IMM and/or systemic corticosteroids use (IMM with systemic corticosteroids, IMM without systemic corticosteroids, systemic corticosteroids without IMM, and neither IMM nor systemic corticosteroids) will be tabulated.

8.0 Patient Disposition

Subject accountability overall and by current investigator will be summarized with number and percentage of subjects.

[figure not shown]
Subjects with any dose adjustments will be summarized as follows:

- Total number and percentage of subjects with EOW vs EW at Baseline
- Number and percentage of subjects with at least one dose escalation (EOW to EW)
- Number and percentage of subjects with EW dosing (i.e., those who started on EW or who escalated to EW) with at least one de-escalation (EW to EOW)
- Number and percentage of subjects who de-escalated from EW to EOW with at least one re-escalation afterwards (EOW to EW)

Subject final status including the following categories will be summarized by number and percentage:

- Subjects who completed the study (defined as: either completed Week 288 or switched to adult care or to commercial Humira), also by sub-category of completion:
 - Completed Week 288
 - Switched to adult care
 - Switched to commercial Humira
- Subjects who discontinued

In addition, the reasons for premature discontinuation of study drug (primary reason and all reasons) will be summarized with frequencies and percentages. Subjects may have

multiple reasons for prematurely discontinuing study drug, but will be counted only once for the primary reason.

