The study will include an open-label period of approximately 298 weeks. Prior to Amendment 4, all subjects were minimally on open label 0.6 mg/kg (maximum of 40 mg) eow of adalimumab beginning at the Baseline visit. After Amendment 4, all subjects will be on open label 20 mg, 40 mg or 80 mg eow of adalimumab. A 70-Day Follow-Up phone call will be completed for all subjects who either terminate early from the study or who complete the study.

Criteria for Evaluation:

Efficacy:

This study will utilize the PMS (and Mayo score if available) and PUCAI to determine efficacy of the study drug.

The following efficacy endpoints will be analyzed using summary statistics:

- The proportion of subjects who achieve clinical remission as measured by PMS (defined as a PMS ≤ 2 and no individual subscore > 1) over time;
- The proportion of subjects who achieve clinical response as measured by PMS (defined as a decrease in PMS ≥ 2 points and ≥ 30% from Baseline) over time;
- The proportion of subjects who achieve PUCAI remission (defined as < 10) over time;
- The proportion of subjects who achieve PUCAI response (defined as a decrease in PUCAI ≥ 20 points from Baseline).

Efficacy will also be evaluated based on other measures of disease activity, including IMPACT III, WPAI, z-score for height and weight, bone age, BMI, and laboratory values as applicable. The proportion of subjects who achieve remission/response based on Mayo score and mucosal healing based on Mayo endoscopy subscore will be summarized for subjects with available Mayo score.

Pharmacokinetic and Immunogenicity:

As appropriate, population pharmacokinetic analysis and/or any additional analyses may be performed on samples for serum adalimumab concentrations and immunogenicity status collected prior to Amendment 2.

Adalimumab M10-870 Protocol Amendment 5 EudraCT 2015-001346-29

Criteria for Evaluation (Continued):

Safety:

Safety analyses will be performed on all subjects who receive at least one dose of study drug. Incidence of AEs, changes in vital signs, physical examination results, and clinical laboratory data will be assessed.

Statistical Methods:

[figure not shown]

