Ongoing subjects will continue to administer the remainder of dispensed vials as per the dose regimen prior to Amendment 4 until their first visit with Study Drug Dispensing after Amendment 4 when they will transition to the fixed dose regimen.

[figure not shown]
The duration of the study could be up to 298 weeks, which includes a 288-week open-label maintenance period and a 70-day follow-up. There is a \pm 3 day window for all study visits. An effort will be made to bring subjects back to their original scheduled visit (calculated from Baseline) if they are out of the visit window.

Efficacy and safety measurements will be performed throughout the study (see Table of Activities, Section 5.3.1). Clinical evaluation will be performed at Baseline, Weeks 4, 8, 12, 24, 36, 48, 60, 72, 84, 96, 108, 120, 144, 168, 192, 216, 240, 264 and 288/Premature Discontinuation and unscheduled Visits. Subjects may undergo an optional endoscopy during Weeks 48, 96, 192, and 288/Premature Discontinuation Visit to assess disease activity and for surveillance per the investigator's discretion.

Treatment of Subjects with a Disease Flare

Criteria for Disease Flare are as follows:

- Subjects with a Baseline Study M10-870 PMS of 0 to 2 who present with a PMS at least 3 points greater than their Baseline Study M10-870 score.
- Subjects with a Baseline Study M10-870 PMS of 3 to 4 who present with a PMS at least 2 points greater than their Baseline Study M10-870 score.
- Subjects with a Baseline Study M10-870 PMS of 5 to 6 who present with a PMS at least 1 point greater than their Baseline Study M10-870 score.
- Subjects who present with a PMS of at least 2 points greater than their PMS at the previous visit and who are not in remission per PMS.

Prior to Amendment 4:

- Subjects with a disease flare who were on 0.6 mg/kg (maximum dose of 40 mg, weight based) eow of adalimumab could receive 0.6 mg/kg (maximum of 40 mg, weight based) ew of adalimumab.
- Subjects with a disease flare who were on 0.6 mg/kg ew of adalimumab could receive 40 mg ew (maximum dose of 40 mg).

Subjects with persistently uncontrolled disease while on adalimumab 40 mg ew (max dose) were to be discontinued from the study.

After Amendment 4:

[figure not shown]
- Subjects who are on 20 mg eow of adalimumab may receive 40 mg eow of adalimumab.
- Subjects who are on 40 mg eow of adalimumab may receive 80 mg eow of adalimumab.

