3.0 Introduction

This statistical analysis plan (SAP) will provide details to further elaborate statistical methods as outlined in the protocol of Study M10-870, "A Multi-Center, Open-Label Study of the Human Anti-TNF Monoclonal Antibody Adalimumab to Evaluate Long-Term Safety and Tolerability of Repeated Administration of Adalimumab in Pediatric Subjects with Ulcerative Colitis Who Completed the Study M11-290" and describe analysis conventions to guide the statistical programming work. The analysis plan is based on the study protocol Amendment 3 dated 30 July 2019.

The analyses for the Japan Sub-Study will be described in a separate SAP. All described analysis in this SAP will be for subjects enrolled outside of Japan.

The statistical analysis will be performed using the SAS® software version 9.2 or later.

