4.2 Design Diagram

This study is a Phase 3, multi-center, open-label study designed to evaluate the long-term maintenance of clinical response, safety and tolerability of ADA in pediatric subjects with ulcerative colitis.

Subjects are eligible to enroll in the Study M10-870 if they have successfully completed Protocol Study M11-290 through Week 52 and meet all of the inclusion criteria and none of the exclusion criteria for Study M10-870.

The Week 52 visit from the Study M11-290 serves as the Baseline Visit for subjects entering Study M10-870.

All subjects receive open-label therapy as follows beginning at the Baseline Visit in Study M10-870:

- Subjects who enroll into the study from blinded treatment in Study M11-290 receive open label 0.6 mg/kg (maximum of 40 mg) every other week (EOW) of adalimumab
- Subjects who received open label 0.6 mg/kg (maximum of 40 mg) every week (EW) of adalimumab in Study M11-290 maintain the same dose in Study M10-870

Subjects who demonstrate a disease flare may have their dose escalated. Subjects who have been in remission (PMS \leq 2 with no individual subscore > 1) for at least 8 weeks and for at least 2 consecutive visits may have their dosage de-escalated. Subjects who demonstrate disease flare after dose de-escalation have an opportunity to re escalate their dose back to adalimumab every week (EW) dosing.

[figure not shown]
Subjects with persistently uncontrolled disease while on adalimumab 40 mg EW (maximum dose) are to be discontinued from the study.

The duration of the study is up to 298 weeks (approximately 5.5 years).

More details are described in the protocol, including the Study Activities table.

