4.3 Sample Size

Subjects who successfully completed Study M11-290 through Week 52 are potentially eligible to participate in this study. Originally, based on an expected number of 155 subjects being re-randomized at Week 8 of the parent study, an expected Study M11-290 completion rate of 66% and a roll-over rate of 80% of eligible subjects (based on previous experience with the pediatric CD Studies M06-806 and M06-807) it was expected that approximately 85 subjects from Study M11-290 would enroll into the

main Study M10-870 study and 8 subjects from the Japanese sub-study. However, as per Study M11-290 protocol Amendment 5 the parent study will be closed with N = 101 (N = 93 in main study + N = 8 in Japan sub-study) and the expected sample size in Study M10-870 is approximately 60 subjects (55 Ex-Japan and 5 in Japan).

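### SAP 8.0 defines dose adjustments only as EOW/EW changes, so escalations, de-escalations and re-escalations on the post-Amendment 4 fixed-dose regimen have no row

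*SAP*

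**What the plan says.** SAP 3.0 fixes its reference version: "The analysis plan is based on the study protocol Amendment 3 dated 30 July 2019". SAP 12.0 records no later changes.

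SAP 8.0 opens the table with "Subjects with any dose adjustments will be summarized as follows". Four rows follow. The first is a status, EOW or EW at Baseline. The other three are adjustments:

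- escalation: "Number and percentage of subjects with at least one dose escalation (EOW to EW";
- de-escalation among subjects with EW dosing: "with at least one de-escalation (EW to EOW";
- re-escalation, again EOW to EW, among those who had de-escalated.

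The current protocol (Amendment 5, which carries the Amendment 4 dosing) states in the Synopsis: "After Amendment 4, all subjects will be on open label 20 mg, 40 mg or 80 mg eow of adalimumab". Under Protocol 5.1, ongoing subjects keep the old regimen "until their first visit with Study Drug Dispensing after Amendment 4 when they will transition to the fixed dose regimen". Protocol 5.5.1 then gives the steps after Amendment 4: 20 to 40 mg or 40 to 80 mg eow for flare, the next lower dose for sustained remission, and the next higher dose for a flare after de-escalation.

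**The concern.** The table claims to cover any adjustment, but its row definitions belong to a regimen that ongoing subjects leave at their first dispensing visit after Amendment 4. From then on an adjustment is a change of milligrams at constant frequency, which the rows do not describe. A reader of the study report would see how many children moved between EOW and EW, and nothing about how many needed a higher fixed dose or were stepped down. In a long-term extension whose objective includes maintenance of response, that is useful context for the remission and response proportions.

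A second problem concerns labels. A subject on weekly dosing who is moved to the fixed regimen goes from EW to EOW in the literal sense of the de-escalation row, although the move has nothing to do with remission.

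**Working it through.** The plan gives no figure to reproduce here. The check maps each dose change in the protocol, by frequency before and after, onto the SAP 8.0 rows. The rule is: EOW to EW goes to the escalation or re-escalation row; EW to EOW goes to the de-escalation row; anything else has no row.

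| Change (Protocol 5.1, 5.5.1) | Frequency | SAP 8.0 row |
|---|---|---|
| Before A4, flare: 0.6 mg/kg eow to ew | EOW to EW | escalation |
| Before A4, flare: 0.6 mg/kg ew to 40 mg ew | EW to EW | none |
| Before A4, remission: ew to eow | EW to EOW | de-escalation |
| Before A4, re-escalation: eow to ew | EOW to EW | re-escalation |
| After A4, flare: 20 to 40 mg; 40 to 80 mg | EOW to EOW | none (2 steps) |
| After A4, remission: 80 to 40 mg; 40 to 20 mg | EOW to EOW | none (2 steps) |
| After A4, re-escalation: 20 to 40 mg; 40 to 80 mg | EOW to EOW | none (2 steps) |
| Compulsory switch of an EOW subject | EOW to EOW | none |
| Compulsory switch of an EW subject | EW to EOW | de-escalation, read literally |

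Before Amendment 4, 3 of 4 steps have a row. The missing one is a separate small gap not caused by Amendment 4. On the fixed-dose regimen, 0 of 6 steps have a row.

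**Is the gap filled elsewhere?** No. SAP 9.0 summarizes exposure in days and compliance as injections received over injections planned. Neither shows dose level, and no other SAP section tabulates it.

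**How many subjects could be affected?** SAP 4.3 gives the ceiling: "the expected sample size in Study M10-870 is approximately 60 subjects (55 Ex-Japan and 5 in Japan". The SAP covers only the ex-Japan subjects, so the range is 0 to about 55, and one subject is 1/55 = 1.8 percentage points if the denominator is 55.

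A date bound narrows this. The switch needs a dispensing visit, and the last scheduled one in Protocol Table 1 is Week 264. Amendment 4 is dated 13 January 2021, and 264 × 7 = 1,848 days earlier is 23 December 2015. Apart from unscheduled dispensing, the switch can reach only subjects with Baseline after about that date. Ethics approval must come first and its timing is not given. If it took 8, 13 or 26 weeks (assumption), the cut-off becomes 17 February, 23 March or 22 June 2016. Baseline dates are not in the documents.

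Flare steps can arise only from 20 or 40 mg eow, that is, in subjects under 40 kg or already stepped down. Remission steps can arise only from 40 or 80 mg.

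**Can the steps be told apart?** Protocol 5.3.1.1 has weight recorded at each site visit to determine the dose. If a growing child is moved up a band on that basis, the dose goes from 20 to 40 mg at 25 kg or from 40 to 80 mg at 40 kg. These are the same dose pairs as the flare steps, so a count by dose alone would mix growth with flare.

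**The case against.** The strongest reply is that this is version lag, openly declared. The SAP names Amendment 3 as its basis, also serves the interim analysis, and under Protocol 8.1 need be final only before database lock. A later version may exist. That is fair, and the point applies only to the SAP provided, but in that SAP the gap is real.

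A reader might infer that the table would report zero fixed-dose escalations. It would not: the rows carry EOW and EW labels, so the table is silent on fixed-dose steps.

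A reader might also infer that weekly-dosed subjects will be counted as de-escalated at the switch. The row label permits that, but SAP 4.2 limits de-escalation to subjects in remission, at least 8 weeks and "for at least 2 consecutive visits may have their dosage de-escalated". Protocol 5.5.1 adds medical monitor approval. What stands is that SAP 8.0 does not repeat the condition, so one clarifying sentence is needed.

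Nor do the documents require a row for the compulsory switch. The protocol speaks of adjusting dosage in connection with flare, and a sponsor-wide regimen change can reasonably be left out. Showing it is a reporting choice.

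Finally, few steps may occur. Clinic visits are 24 weeks apart after Week 120, and the study may conclude early under Protocol 5.4.2. That limits the size of the gap but does not remove it.

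**Conclusion.** The point holds as a minor reporting gap. SAP 8.0 promises a summary of any dose adjustments, and its definitions omit every flare-driven escalation, remission-driven de-escalation and re-escalation on the fixed-dose regimen. They also leave the label of the EW subject's switch to be settled by reference to other sections.

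The size cannot be computed: the documents do not say how many subjects were still on study at Amendment 4 or how many later changed dose. The conclusion rests on two assumptions: that the SAP provided is the one to be applied, and that at least some ongoing subjects switched, as the protocol expects.

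It would be wrong to infer from this that the efficacy results are affected. The PMS and PUCAI definitions do not use this table, and SAP 10.1 plans no confirmatory testing. No view is taken on which dose or clinical rule is right.

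**What to change.** Before database lock, align SAP 8.0 with the current protocol:

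1. Count escalation, de-escalation and re-escalation by dose level as well as frequency, using the protocol's own steps, separately before and after Amendment 4.
2. State that the compulsory Amendment 4 switch is not counted as an escalation or a de-escalation. Showing it as its own category is optional.
3. Keep changes due only to crossing a weight band out of these counts. Use the weight at the visit together with the recorded reason for the change. Where no reason is recorded, use the visit PMS against the protocol's flare and remission criteria. Weight alone does not settle a visit at which a band crossing and a flare coincide.

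The cost is a short SAP amendment and one reprogrammed descriptive table. Dose, date, weight and PMS are already collected under Protocol 5.3.1.1. The documents do not show whether a reason for each change is recorded, which is why item 3 needs the PMS fallback. No new data collection is needed.

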5.5.1 Treatments Administered

Prior to Amendment 4, all subjects received open-label therapy as follows beginning at the Baseline Visit in Study M10-870:

- Subjects who enrolled into the study from blinded treatment in Study M11-290 were to receive open label 0.6 mg/kg (maximum of 40 mg) eow of adalimumab.
- Subjects who received open label adalimumab in Study M11-290 were to maintain the same dose in Study M10-870.

After Amendment 4, ongoing subjects will be switched to receive a fixed dose regimen, by weight cutoff, incorporating open-label citrate free adalimumab in PFS (20 mg, 40 mg, or 80 mg) as follows:

• Subjects with a body weight < 25 kg will receive open label 20 mg eow of adalimumab

- Subjects with a body weight \geq 25 kg < 40 kg will receive open label 40 mg eow of adalimumab
- Subjects with a body weight ≥ 40 kg will receive open label 80 mg eow of adalimumab

Treatment of Subjects with Disease Flare

Prior to Amendment 4:

- Subjects who were on 0.6 mg/kg (maximum dose of 40 mg, weight based) eow of adalimumab could receive 0.6 mg/kg (maximum of 40 mg, weight based) ew.
- Subjects who were on 0.6 mg/kg ew of adalimumab could receive 40 mg ew (maximum dose) of adalimumab.

[figure not shown]
Subjects with persistently uncontrolled disease while on adalimumab 40 mg ew (max dose) were to be discontinued from the study.

After Amendment 4:

- Subjects who are on 20 mg eow of adalimumab may receive 40 mg eow of adalimumab.
- Subjects who are on 40 mg eow of adalimumab may receive 80 mg eow of adalimumab.

Subjects with persistently uncontrolled disease while on adalimumab 80 mg eow should be discontinued from the study.

Consideration should be given to have the subject return to the study site for unscheduled visit in order to collect the required PMS to satisfy the definition of disease flare.

Criteria for Disease Flare are as follows:

- Subjects with a Baseline Study M10-870 PMS of 0 to 2 who present with a PMS at least 3 points greater than their Baseline Study M10-870 score.
- Subjects with a Baseline Study M10-870 PMS of 3 to 4 who present with a PMS at least 2 points greater than their Baseline Study M10-870 score.
- Subjects with a Baseline Study M10-870 PMS of 5 to 6 who present with a PMS at least 1 point greater than their Baseline Study M10-870 score.
- Subjects who present with a PMS at the current visit of at least 2 points greater than their PMS at the previous visit and who are not in remission per PMS.

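### SAP 8.0 was not updated for Amendment 4: its EOW/EW rows miss every fixed-dose step and the earlier step to 40 mg ew, and leave the mandated switch open to being counted as a de-escalation

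*SAP*

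**What the plan says.** SAP 8.0 (Patient Disposition) describes dose adjustment by dosing frequency. After a row for EOW versus EW at Baseline, it has three rows for changes:

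- Escalation: "Number and percentage of subjects with at least one dose escalation (EOW to EW)".
- De-escalation, among subjects ever on EW: "with at least one de-escalation (EW to EOW)".
- Re-escalation, among those who de-escalated: "Number and percentage of subjects who de-escalated from EW to EOW with at least one re-escalation afterwards (EOW to EW)".

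There is no other dose-change category. SAP 3.0 gives the reason: "The analysis plan is based on the study protocol Amendment 3 dated 30 July 2019". SAP 4.2 accordingly says that subjects who flare after a de-escalation "have an opportunity to re escalate their dose back to adalimumab every week (EW) dosing". SAP 12.0 records no changes.

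The current protocol differs. Protocol 5.5.1 states: "After Amendment 4, ongoing subjects will be switched to receive a fixed dose regimen, by weight cutoff". The bands are 20 mg eow below 25 kg, 40 mg eow from 25 to below 40 kg, and 80 mg eow from 40 kg. The Synopsis (Duration of Treatment) confirms that no weekly regimen remains. After the switch, a flare is treated by going from 20 to 40 mg eow, or: "Subjects who are on 40 mg eow of adalimumab may receive 80 mg eow of adalimumab". De-escalation and re-escalation go to the next lower or next higher dose. Before the switch there was also a second flare step within weekly dosing: "Subjects who were on 0.6 mg/kg ew of adalimumab could receive 40 mg ew (maximum dose) of adalimumab".

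**The concern.** The row definitions belong to a regimen that the protocol has since replaced. A programmer who applies them as written to the final data would find no dose adjustments at all during the fixed-dose period. The mandated change from a weekly to a fixed every-other-week regimen would fit the de-escalation label, whether or not the subject was in remission.

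This table is the planned output that shows how often the dose had to be raised, could be lowered, and had to be raised again. SAP 9.0 summarises exposure in days and compliance by injections, not by dose. The study objective includes maintenance of response, so a reader will want to know how often response was held only after a dose increase.

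**Working it through.** The plan states no figure to reproduce. The check has two parts: apply the SAP 8.0 labels to each dose move the protocol allows, then compare the nominal amount per two weeks before and after the mandated switch.

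**Labels.** EOW to EW is an escalation or re-escalation, EW to EOW is a de-escalation, and anything else is not counted.

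| Move (Protocol 5.5.1) | Frequency | Result under SAP 8.0 |
|---|---|---|
| 0.6 mg/kg eow to 0.6 mg/kg ew (flare, pre-switch) | eow to ew | escalation |
| 0.6 mg/kg ew to 40 mg ew (flare, pre-switch) | ew to ew | not counted |
| ew to eow in remission (pre-switch) | ew to eow | de-escalation |
| Mandated switch from eow | eow to eow | not counted |
| Mandated switch from ew | ew to eow | fits de-escalation |
| 20 to 40 or 40 to 80 mg eow | eow to eow | not counted |
| 80 to 40 or 40 to 20 mg eow | eow to eow | not counted |

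So 0 of the 4 fixed-dose steps are counted.

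**Amount per two weeks.** Inputs are the dose rules in Protocol 5.5.1 and the 14 to 80 kg weight range of Appendix F. The prior amount is min(0.6 × weight, 40) mg on eow, twice that on ew, and 2 × 40 = 80 mg on 40 mg ew. The new amount is 20, 40 or 80 mg. Ratio = new ÷ prior:

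| Weight | from 0.6 mg/kg eow | from 0.6 mg/kg ew | from 40 mg ew |
|---|---|---|---|
| below 25 kg | 1.33–2.38 | 0.67–1.19 | 0.25 |
| 25 to below 40 kg | 1.67–2.67 | 0.83–1.33 | 0.5 |
| 40 kg or more | 2.0–3.33 | 1.0–1.67 | 1.0 |

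Examples on 0.6 mg/kg ew: at 40 kg, 80 ÷ 48 = 1.67; at 50 kg, 80 ÷ 60 = 1.33; at 67 kg, 80 ÷ 80 = 1.0. At 40 kg or more, therefore, no switch from ew lowers the amount, yet each one fits the EW to EOW label. The 0.25 entry needs a child below 25 kg already on 40 mg ew, which is a corner case.

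**The uncounted pre-switch step.** 40 ÷ min(0.6 × weight, 40) is 2.67 at 25 kg (40 ÷ 15), 1.67 at 40 kg (40 ÷ 24), and 1.0 from 66.7 kg (0.6 × 66.7 = 40). Below 66.7 kg it is a real increase. A subject who rolled over on ew and took only this step would appear as never escalated.

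**Re-escalation.** If the switch is read as a de-escalation, a subject whose only EW to EOW move was the switch enters the group eligible for re-escalation. That subject can never be counted as re-escalated, because no weekly regimen remains.

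**The case against.** The strongest reply is that this is a version lag: the labels fit the Amendment 3 regimen on which the SAP says it is based, and Protocol 8.1 allows the SAP to be finalised up to database lock. That explains the fixed-dose gap but does not remove it. It does not explain the missed step to 40 mg ew, which was uncounted under the old regimen too, although SAP 4.2 itself names 40 mg EW as the maximum dose.

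Second, de-escalation already has a meaning. SAP 4.2 ties it to remission for at least 8 weeks and 2 consecutive visits, Protocol 5.5.1 adds medical monitor approval, and the protocol calls the Amendment 4 change a switch or transition. A careful programmer could exclude it on that basis. This stands: counting the switch is a literal reading that 8.0 permits, not one it requires.

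Third, the escalation loss is limited. Subjects of 40 kg or more are switched straight to 80 mg eow, the top dose, so first flare escalations after the switch are possible only below 40 kg. The row counts subjects with at least one escalation, so anyone already counted before the switch is not lost. From 66.7 kg the step to 40 mg ew changes nothing. All of this stands.

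A reader might infer that the table will overstate de-escalations. The documents do not support that: remission-based steps down after the switch are missed, which pulls the other way. Nor do they support a safety concern, since Protocol 5.6.4 reports largely overlapping predicted concentrations for the fixed-dose and mg/kg regimens.

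**Conclusion.** Wrong as written; minor. SAP 8.0 counts none of the steps between 20, 40 and 80 mg eow and omits the step from 0.6 mg/kg ew to 40 mg ew, so escalations are undercounted. Whether the mandated switch counts as a de-escalation is left unclear. If it is counted, a same or higher amount at 40 kg or more (1.0 to 1.67 times) would be shown as a reduction. If it is not, true post-switch de-escalations are still missed. The net direction for that row therefore depends on the reading.

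The size in subjects cannot be stated: the documents give neither the number on ew at the switch nor the weight mix at that time. The ratios are nominal amounts under the protocol's dose rules, not exposure. All analyses are descriptive, and no efficacy endpoint, adverse-event rate or test uses this table.

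**What to change.** Before database lock, bring SAP 8.0 into line with the current protocol:

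- (a) Exclude the mandated switch from the escalation, de-escalation and re-escalation counts. Tabulate it separately by prior regimen (0.6 mg/kg eow, 0.6 mg/kg ew, 40 mg ew) and weight band.
- (b) After the switch, count steps between 20, 40 and 80 mg eow made under the flare or remission rules of Protocol 5.5.1. Use recorded dose, PMS and weight to separate steps due only to growth across 25 or 40 kg.
- (c) Before the switch, count 0.6 mg/kg ew to 40 mg ew as an escalation where the dose rises, that is, below about 66.7 kg.

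The cost is a SAP text edit, one additional disposition table and some derivation work. The dosing-log items listed in Protocol 5.3.1.1 include the dose but no reason for a change, so cause has to be derived from the PMS and weight histories. No protocol amendment, extra visit or extra patient is needed. If a later SAP exists, it is enough to confirm that it covers (a) to (c).
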